13.2 Missing Data

The amount and nature of missing data will be characterized and no method of imputation will be used for missing data. A summary of missing data will be provided according to the number of subjects, the time points where the data are missing, and clinical center. For each clinical center, the number and percent of subjects with no missing data will be presented in tabular form.

13.3 Descriptive Analyses

Measured outcome variables will be summarized overall and by relevant demographic and baseline variables. Descriptive statistics such as frequencies and relative frequencies will be computed for all categorical variables. Numeric variables will be summarized using simple descriptive statistics such as the mean, standard deviation and range. A variety of graphical techniques will also be used to display data, ex. histograms, boxplots, scatterplots, etc.

13.4 Phase I

The primary objective of the Phase I part of this study is to determine the MTD of the proposed regimen defined as the dose of carfilzomib added to standard R-ICE chemotherapy which, if exceeded, would put the patient at an undesirable risk of medically unacceptable, DLTs experienced during treatment with C-R-ICE within the treated patient population. The definition of a DLT is in **Section 7.4.1**.

The basic design of the Phase I trial will utilize a standard 3+3 dose-finding scheme which is a special case of the A + B design described by Lin and Shih (2001). Rationale behind the design is nested in the assumption that both the probabilities of toxicity and efficacious response are continuous monotonic non-decreasing functions of the dose.

13.5 Phase Ib (expansion cohort)

The objective of the Phase Ib component is examination of the efficacy and toxicity of the addition of carfilzomib to R-ICE at the MTD dose.

The primary objective of the Phase Ib component is to assess the efficacy of the study treatment arm as compared to historical control. The primary efficacy endpoint will be best overall response rate (PR+CR) within following 3 cycles of C-R-ICE therapy (as demonstrated by whole body PET-CT and dedicated CT scans following Cycle 3 of therapy).

The efficacy analysis will include patients treated in the Phase I and Phase Ib part of the study. This change in the protocol was decided based on the excellent ORR observed in the first 15 patients treated in the Phase part of the study and changes in the protocol budget.

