3.2. Phase Ib Primary Objectives (Expansion cohort)

- To evaluate the safety of carfilzomib (given at maximum tolerated dose [MTD] as determined in Phase I of this study) in combination with R-ICE salvage therapy in relapsed/refractory DLBCL patients.
- To achieve an overall response rate (CR and PR) of 70% after 3 cycles of C-R-ICE in patients between the ages of 18 to 75 with relapsed/refractory CD20-positive DLBCL previously treated with rituximab-based immunochemotherapy (e.g., R-CHOP, R-EPOCH, R-HyperCVAD, etc.) induction.

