9 STUDY PROCEDURES

9.1 Subject Registration

All data management will be conducted at Roswell Park. Eligible patients will be entered on study centrally at the institute by the Study Coordinator. Following registration, patients should begin protocol treatment within 14 days or sooner if clinically necessary. Issues that would cause treatment delays should be discussed with the Principal Investigator at Roswell Park (or

designee). If a patient does not begin protocol therapy within 14 days following registration, the patient's registration on the study may be canceled. The Study Coordinator should be notified of cancellations as soon as possible.

Table 3. Study Calendar

Tests and Observations	Prior to Study ¹	Day 1 of Each Cycle ²	At Time of Restaging ³	Collect Stem Cell and ASCT Data (if applicable) ²⁰	Collect Post ASCT Day +100 Data ²⁰	Post Treatment Follow-Up ⁴
History and Physical Exam	X	X				X
Pulse, Blood Pressure	X	X				X
Height/Weight/Body Surface Area⁵	X	X				
Performance Status	X	X				X
Drug Toxicity Assessment		X				X ⁷
Laboratory Studies						
CBC, Differential, Platelets	X	X ⁸				X
Serum Creatinine, BUN	X	X ⁹				X
Creatinine Clearance (Appendix C)	X	X ⁹				
Serum Electrolytes	X	X ⁹				X
Ca⁺⁺, Potassium	X	X ⁹				X
ALT, AST, Alkaline Phosphatase, Bilirubin	X	X ⁹				X
Phosphorus	X	X ⁹				
LDH and Uric Acid	X	X ⁹				X
EKG	X					
MUGA or ECHO	X					
HBsAg, HBcAb¹⁰	X					
HBV DNA, Qualitative	X ¹⁰					
HCV Ab	X ¹¹					
HIV (If risk factors present)	X					
Beta-2-microglobuline (B2M)	X					
Albumin	X	X				X

Serum or Urine-βHCG (female patients)	X ¹²					
Staging						
Lumbar Puncture	X ⁷	X ¹³				X ¹³
CT Scan (Chest/Abdomen/Pelvis) and/or PET	X ⁶		X			X ²³
Bone Marrow Aspiration and Biopsy	X ²¹		X ¹⁴			X ¹⁴
Histologic Review	X ²²					X ¹⁵
Cytogenetics (e.g., Bcl-2 or c-MYC studies)	X					X ¹⁵
Sample Submission and Correlative Studies						
Lymph Node Biopsy		X ^{16,17}				
Immune Biomarker Samples		X ¹⁸				
Pharmacokinetic /Pharmacodynamic Samples²⁴			X ¹⁹			
Adverse Events	X	X	X			X ⁷

- 1 To be completed within 28 days prior to enrollment
- 2 Within 48 hours prior to Day 1 of each induction treatment cycle.

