10 EFFICACY EVALUATIONS

10.1 Objectives

One of the secondary objectives of this clinical study is to evaluate the overall response rate and complete response rate to C-R-ICE in rel/ref DLBCL. It is important to evaluate response to therapy using standardized response criteria utilized in previous clinical studies in DLBCL patients so direct comparisons can be performed with historical controls (i.e., R-ICE). For this reason response to therapy will be evaluated using the response criteria reported by Cheson published in 2007 which incorporate whole body PET scan in addition to CT scanning.

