10.2 Imaging, Laboratory and Pathological Studies

Imaging, laboratory and pathological studies will be conducted for staging and response evaluation at baseline, between Cycle 2 Day 15 and Cycle 2 Day 28, and at the end of study evaluation following Cycle 3. Response to treatment will be evaluated according to the International Working Group Response criteria as reported by the revised Cheson criteria (Section 10.3).

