13.5.2 Phase Ib Decision Rules

Let π represent the proportion of the evaluable population of interest who experience an overall response within 3 weeks after completion of therapy (i.e., 3 cycles) at the carfilzomib MTD. If the response rate of less than 50% is considered unacceptable. A response rate of more than 70% is considered promising and evidence of such will deem the treatment worthy of further study. The null and alternative hypotheses corresponding to the design are

$$H_0 : \pi \leq 50\%,$$
$$H_a : \pi > 50\%.$$

A total of up to 30 evaluable patients will be accrued in the Phase I and Phase Ib portions of the study. The evaluable population is defined as patients who meet eligibility requirements and complete at least 1 cycle of therapy. Unevaluable patients will be replaced.

With this re-design, the probability is 4.8% of falsely concluding that the proportion of those who experience an overall response exceeds 50% and 80.1% is the probability of correctly concluding efficacy when the overall response rate is 70%.

In the event that the actual first stage sample size is not as planned, the adjustment of the first-stage stopping rule will be based on the approximate minimax rule proposed in Green and Dahlberg (1992): Stop the trial if the number of responses is α or less, where α is the largest value for which power properties would be maintained given the attained first-stage sample size, assuming the planned final sample size is achieved and one applies the planned final boundary. If the planned second stage sample size is not attained, the bound will be adjusted so to preserve Type I error.

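### The primary response endpoint is worded inconsistently, so a patient who responds at the Cycle 2 scan and progresses before the post-Cycle 3 scan could be counted as a success, a failure or missing

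*Combined protocol and SAP*

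**What the plan says.** The endpoint appears in three forms.

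- **Objective** (Section 3.2 and the synopsis objectives): "To achieve an overall response rate (CR and PR) of 70% after 3 cycles of C-R-ICE".
- **Analysis text** (Section 13.5 and the synopsis statistical section): "The primary efficacy endpoint will be best overall response rate (PR+CR) within following 3 cycles of C-R-ICE therapy", followed in the same sentence by "as demonstrated by whole body PET-CT and dedicated CT scans following Cycle 3 of therapy".
- **Tested parameter** (Section 13.5.2): the proportion of evaluable patients who "experience an overall response within 3 weeks after completion of therapy", where therapy means three cycles.

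Section 10.2 schedules response assessment at baseline and then "between Cycle 2 Day 15 and Cycle 2 Day 28, and at the end of study evaluation following Cycle 3", so there are two on-study looks. The Table 3 imaging row is labelled "CT Scan (Chest/Abdomen/Pelvis) and/or PET", which is looser than the imaging named in Section 13.5.

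Three further provisions bear on counting. Section 10.4 restricts follow-up after progression to survival. Section 13.2 rules out imputation. Section 13.5.2 makes an eligible patient evaluable once one cycle is complete. Section 10.1 adds a separate inconsistency about the endpoint's status: "One of the secondary objectives of this clinical study is to evaluate the overall response rate".

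**The concern.** A best-response endpoint normally credits the better of several assessments. A post-Cycle 3 endpoint credits one. With a scheduled Cycle 2 look, the two give different answers for a patient who responds early and then progresses. The plan does not say which applies, nor how to count a patient with no post-Cycle 3 scan.

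This matters more than usual here because the trial is open-label and single-arm, and responses are already known. Section 13.1.2 reports a 90% response rate in Phase I, Section 13.5 says the redesign followed results in the first 15 patients, and the Phase I patients enter the efficacy analysis. An unsettled definition leaves room to settle it after the data have been seen.

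**Working it through.** **1. One patient under each reading.** Take an evaluable patient with a PR at the Cycle 2 scan who progresses before the post-Cycle 3 scan.

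| Reading | Basis | Count |
|---|---|---|
| Best response over the treatment period | 13.5, main clause | Success |
| Response on the post-Cycle 3 scans | 3.2; 13.5, parenthesis | Failure |
| Response experienced by a deadline | 13.5.2 | Success if any response up to three weeks after therapy counts; failure if the three weeks is the window for the post-Cycle 3 scan |
| No post-Cycle 3 scan obtained | 10.4, 13.2 | Missing, with no rule for the denominator |

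Section 10.3.5 starts response duration when CR or PR is first recorded, so a Cycle 2 response is a recorded response. No section says whether it suffices for the primary endpoint.

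**2. Effect on the estimate.** One patient in 30 is 1/30 = 3.3 percentage points. Suppose 19 of 30 respond after Cycle 3 and one more responds only at Cycle 2. The rate is 20/30 = 66.7% on best response, 19/30 = 63.3% on post-Cycle 3 response, and 19/29 = 65.5% if that patient is dropped as missing.

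**3. The plan's own figures.** Section 13.5.2 gives a type I error of 4.8% and power of 80.1% for 50% versus 70% with up to 30 evaluable patients, but no cut-off. With X binomial(30, p), the chance of success at cut-off r is P(X ≥ r) = Σ C(30,x) pˣ(1−p)³⁰⁻ˣ, summed over x = r to 30.

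| Cut-off | Type I error (p = 0.50) | Power (p = 0.70) |
|---|---|---|
| 19/30 | 10.0% | 84.1% |
| 20/30 | 4.9% | 73.0% |
| 21/30 | 2.1% | 58.9% |

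No cut-off at 30 reproduces the stated pair. A rule of at least 20 of 30 is used below because it is the lowest cut-off with type I error under 5%. It is an assumption, not the plan's rule.

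**4. Illustration of the false-positive chance.** Let the true post-Cycle 3 rate be 50%, and let a share q respond only at Cycle 2. The best-response rate is then 0.50 + q, and the chance of declaring success is P(X ≥ 20) at that rate.

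| q (assumed) | Best-response rate | P(X ≥ 20 of 30) |
|---|---|---|
| 0 | 50% | 4.9% |
| 2% | 52% | 7.6% |
| 3% | 53% | 9.3% |
| 5% | 55% | 13.5% |

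The documents give no value for q.

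**5. Imaging.** Section 10.3.1 allows CR with a residual mass of any size if it is PET-negative, in a patient whose pre-treatment PET was positive. Section 10.3.2 requires at least a 50% fall in the summed products of diameters for PR. A residual mass that has shrunk by less than half could thus be a response when PET is done and not when only CT is done, so the calendar's looser label can affect the count.

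**The case against.** The strongest reply is that the Section 13.5 sentence, read to its end, requires the response to be shown on scans after Cycle 3. That agrees with the objective, and the three weeks in Section 13.5.2 can be taken as the scan window. All three wordings then describe one assessment, and an early responder who progresses is not a success. Section 8.5 also calls for end-of-study evaluations when treatment stops, so a progressing patient may well be scanned.

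Much of this stands. A reader might infer that the plan counts early responders who progress as successes. The documents do not support that as a settled rule; it is one permitted reading. But the parenthesis does not remove the ambiguity: the word best has little meaning if only one assessment counts, and Section 8.5 does not say that a discontinuation evaluation serves as the post-Cycle 3 assessment.

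A reader might also infer that the test against 50% is biased toward success. That does not follow either. Section 13.5.1 attributes the 50% only to historical information. Section 1.2 describes a salvage trial giving three cycles, with 51% response after prior R-CHOP, but says neither how response was timed nor that it is the source of the benchmark. If the benchmark was itself a best-response rate, best response here would be like for like.

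On imaging, the calendar label is one row covering baseline, restaging and follow-up, while Section 13.5 is specific to the endpoint, and the response criteria already provide for a negative or absent pre-treatment PET. This is a reconciliation point, not evidence of mis-scoring.

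**Conclusion.** The point holds as an inconsistency in the primary endpoint text that should be reconciled. The plan permits different counts for the same patient and has no rule for a response seen only at Cycle 2 or for a missing post-Cycle 3 scan. Each affected patient is worth 3.3 points of response rate at 30 patients.

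The rise in false-positive chance from 4.9% to between 7.6% and 13.5% is illustrative. It rests on three assumptions: a cut-off of 20 of 30, an interim-only share of 2% to 5%, and a 50% benchmark that is a post-Cycle 3 rate. None is stated in the documents. It shows that a small share of such patients would matter, not that the trial's error rate is inflated.

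**What to change.** Use one definition in the synopsis, 3.2, 13.5 and 13.5.2: CR or PR at the post-Cycle 3 assessment before transplant, within one stated scan window reconciled with the three weeks in 13.5.2. State that evaluable patients who progress, die, start new therapy or have no post-Cycle 3 assessment stay in the denominator as non-responders. Report best response, including responses seen only at Cycle 2, as a secondary result. Reconcile the Table 3 imaging row with the imaging named in 13.5, and the endpoint's status in 10.1 with 3.2 and 13.5.

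Record that the clarification was made after Phase I responses were known. Adding non-responder rules now is itself a change made with data in view, and reporting both rates lets readers see whether it matters.

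The cost is wording. Section 13.5 already calls for the scans, and the planned sample size and nominal error rates do not change. The reported response rate may be slightly lower.

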13.1.2 Phase Ib

The sample size calculation for the Phase Ib population is based on testing the hypotheses concerning the proportion of the population who experience an objective response (i.e., CR or PR) described above. This design requires a total of up to 30 patients in order to achieve approximately 80.1% power to detect differences of 20 percentage points (50% versus 70%).

Based on the excellent response observed in the patients treated in the Phase I portion (ORR 90%) and budget changes, the sample size for the Phase Ib portion was reduced. The phase Ib portion will include 9 additional patients. The efficacy analysis will include evaluable patients in the Phase I and Phase Ib portions combined (sample size up to 45). The sample size calculation for the efficacy analyses is based on testing the hypotheses concerning the proportion of the population who experience an objective response (i.e., CR or PR) described above. This design requires a total of up to 30 patients in order to achieve approximately 80.1% power to detect differences of 20 percentage points (50% versus 70%).

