13.5.3 Secondary Analyses

Both efficacy and toxicity rates will be estimated using simple relative frequencies. The corresponding 95% confidence intervals for the estimated probabilities will be computed using the method proposed in Clopper and Pearson (1934). The relationship between binary outcomes and collected demographic and baseline variables will be statistically assessed using logistic regression in an exploratory fashion. Maximum likelihood estimation will be utilized in the model fitting procedures as implemented by SAS PROC LOGISTIC. Wald tests of the model effects will be performed to assess statistical significance; see SAS documentation for details. See Hosmer and Lemeshow (2000) for a discussion of such techniques. Alternative parametric models will be considered if model fit is found to be inadequate.

The estimated distributions of overall and progression free survival will be obtained using the Kaplan-Meier method. Estimates of quantities such as median survival will be obtained. Corresponding confidence intervals using the methodology of Brookmeyer and Crowley (1982) will be computed. It is assumed a priori that any drop out times will be non-informative in terms of the censoring mechanism. Groups defined by levels of categorical or dichotomized numeric demographic/baseline variables will be compared in regards to time-to-event distributions using the log-rank test. Cox proportional hazards model regression will be utilized for multivariate analyses.

All tests will be two-sided and tested at a 0.05 nominal significance level. Standard diagnostic plots will be used to assess model fit and transformations of variables may be considered in order to meet statistical assumptions.

The analysis will be performed using the SAS® statistical software system.

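### Phase I patients were added to the efficacy test after their responses had been seen, so the quoted 4.8% error and 80.1% power do not describe the pooled decision

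*Combined protocol and SAP*

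**What the plan says.** Section 13.5 makes overall response the primary efficacy endpoint, judged against a historical rate that Section 13.5.1 sets at 50%. It then says that the efficacy analysis takes in both phases, a change "decided based on the excellent ORR observed in the first 15 patients treated in the Phase part of the study" and also because the budget changed. Section 13.1.2 gives the same two reasons for shrinking the expansion to 9 further patients: "Based on the excellent response observed in the patients treated in the Phase I portion (ORR 90%) and budget changes". It gives no numerator or denominator for the 90%.

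Section 13.5.2 states: "A total of up to 30 evaluable patients will be accrued in the Phase I and Phase Ib portions of the study". For this re-design it says that "the probability is 4.8% of falsely concluding that the proportion of those who experience an overall response exceeds 50"% and that "80.1% is the probability of correctly concluding efficacy when the overall response rate is 70"%. It does not say how many responses are needed for success and makes no allowance for responses already known. It also keeps rules for adjusting a first and a second stage, without stage sizes or boundaries. Section 13.1.2 gives a second pooled total as well, referring to "evaluable patients in the Phase I and Phase Ib portions combined (sample size up to 45").

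**The concern.** The responses that prompted the redesign are also counted in the test that the redesign created. An error rate of 4.8% is a statement about 30 outcomes that are all unknown when the rule is fixed. Here about half of them or more were known, and they helped to decide that they should be included. Budget as a second reason does not remove the dependence, because the plan names the response data as a reason too.

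This is the Phase Ib primary efficacy decision. Someone planning the next trial would read 4.8% as the chance of a false lead and 80.1% as the chance of finding a true 70% rate. The point would remain if every patient had received one dose and the power had been computed correctly.

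**Working it through.** **Inputs.** Null rate 50%, target rate 70%, stated error 4.8% and power 80.1%, one-sided alternative, up to 30 pooled patients (Section 13.5.2). Up to 21 Phase I and 9 Phase Ib patients (Sections 4.2 and 13). Phase I response rate 90% (Section 13.1.2). First 15 patients as the trigger (Section 13.5). No cut-off is stated, so I assume the smallest count with exact one-sided error of 5% or less.

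**1. The plan's own figures.** With X ~ Binomial(30, π), error = P(X ≥ r | 0.5) and power = P(X ≥ r | 0.7):

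| Responses needed | Error | Power at 70% |
|---|---|---|
| 19/30 | 10.0% | 84.1% |
| 20/30 | 4.9% | 73.0% |
| 21/30 | 2.1% | 58.9% |
| 22/30 | 0.8% | 43.2% |

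No row gives 4.8% with 80.1%. Normal approximations at one-sided 5% give power between 65% and 77%. Adding a futility look to a 30-patient design does not raise power above 73.0% at an error of 5% or less. Among designs with one futility look and 20 to 47 patients, only 37-patient designs matched both figures. One example stops at 12/23 or fewer and succeeds at 24/37 or more (4.82% and 80.1%).

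**2. Which count is 90%?** 13/15 = 86.7% and 14/15 = 93.3%, so no count out of 15 gives exactly 90%. 18/21 = 85.7% and 19/21 = 90.5%. The figure may be rounded or may use another denominator, so I carry all four counts.

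**3. Overall false-positive rate.** This needs the rule that would have led to pooling, and none was written. As an illustration, suppose Phase I is pooled if the first 15 have at least c responders, and otherwise Phase Ib is tested alone at 4.8%. At a true 50%:

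error = P(X15 ≥ c) × P(total ≥ 20 | X15 ≥ c) + P(X15 < c) × 0.048

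- c = 9: 0.3036 × 0.1486 + 0.6964 × 0.048 = 7.9%
- c = 10: 0.1509 × 0.2390 + 0.8491 × 0.048 = 7.7%
- c = 12: 0.0176 × 0.5457 + 0.9824 × 0.048 = 5.7%
- c = 13: 0.0037 × 0.7173 + 0.9963 × 0.048 = 5.1%
- c = 14: 0.0005 × 0.8548 + 0.9995 × 0.048 = 4.8%

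If the trigger is applied to all 21 Phase I patients instead, the rate peaks at about 8.5%.

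**4. How much is already settled.** With a 20/30 cut-off and s responders seen, the remaining patients must supply 20 − s. At a true 50% in those patients:

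| Seen | Still needed | Chance of passing |
|---|---|---|
| 13/15 | 7/15 | 69.6% |
| 14/15 | 6/15 | 84.9% |
| 18/21 | 2/9 | 98.0% |
| 19/21 | 1/9 | 99.8% |

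If Phase I ended at 15 patients, then N = 24 and the cut-off is 17. The chance is 74.6% after 13/15 and 91.0% after 14/15.

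**The case against.** The strongest reply has three parts.

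First, the probabilities in step 4 do not measure bias. A fully prespecified 30-patient test with 13/15 responders at its midpoint would have the same 69.6% chance of passing. The early data are also strong evidence in themselves: at a true 50%, 13 or more responders in 15 has a probability of 0.37%. This stands. A reader might set 70% to 99.8% against 4.8% and infer an enormous false-positive rate, but the two are different quantities. The overall rate in step 3 is at most modestly above 5%, and is barely changed for triggers close to the reported result.

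Second, a reader might infer that the 9 Phase Ib patients can hardly change the verdict. That needs about 18 or 19 responders among 21, a count the documents do not give. Section 4.1 does treat Phase I results as available, but Section 13.5 names the first 15 patients. With 13 or 14 of 15 the pooled test still fails 30% or 15% of the time at a true 50%.

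Third, the cut-off is assumed. Section 13.5.2 calls a rate above 70% promising. If success needed an observed rate above 70%, that is 22/30, the chance of passing at a true 50% would be 30% after 13/15, 50% after 14/15 and 91% after 19/21. This also stands, and it is why the cut-off must be written down.

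The plan is open about the data-driven change, aims at estimation for later comparative trials (Section 13) and already plans exact confidence intervals (Section 13.5.3). That makes repair easy. It does not support quoting 4.8% and 80.1% for a rule chosen after the data were seen.

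**Conclusion.** The concern holds. Pooling and the smaller expansion were decided partly on responses already seen and partly on budget, and Section 13.5.2 quotes error rates that ignore this. The true error rate is undefined. Illustrative triggers of 9 to 14 responders in the first 15 put it at about 4.8% to 7.9%, so the inflation may be small. Separately, the quoted pair is not attainable with 30 patients at any cut-off; with error held to 5% or less, power at 70% is 73.0%.

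Much of the outcome was fixed when the change was made, but how much depends on the count behind the 90% and on a cut-off that the plan does not state. The match with a 37-patient two-stage design, together with the leftover stage wording, suggests that the figures were carried over from a different design. That is an inference, and the documents do not say so.

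**What to change.** In Sections 13.1.2, 13.5 and 13.5.2 and in the synopsis:

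1. Give the responders and denominator behind the 90%, the number of patients whose response was known when pooling was decided, and the number of responses required for success.
2. Withdraw 4.8% and 80.1% as properties of the pooled decision, and label the pooled response rate descriptive.
3. Report the response rate with an exact 95% confidence interval separately for patients whose response was known at the decision and for those assessed afterwards. Rest any claim that the regimen merits further study on the second group, with exact operating characteristics for its actual size.

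Two examples of the third step. With 15 later patients (21 + 9 − 15, if both maxima are reached), at least 12/15 gives 1.8% error and power of 30% at a true 70% and 94% at 90%; at least 11/15 would give 5.9% error. If only the 9 Phase Ib patients are untouched, at least 8/9 gives 2.0% error and power of 20% and 77%; at least 7/9 would give 9.0% error.

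The cost is wording and one extra table, with no more patients. The price is a less favourable statement of power, especially at a true rate of 70%.
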